6.1 Background

Norditropin[®] (NN-220; somatropin; Novo Nordisk A/S, Denmark), a recombinant human growth hormone (rhGH) produced by genetic recombinant technology, is currently the sole approved medication for the treatment of short stature due to NS in France. In October 2020, the Transparency Committee (CT- *Commission de Transparence*) rated the actual clinical benefit (SMR- *Service Medical Rendu*) of Norditropin[®] as “important” and issued a favourable opinion for inclusion of Norditropin[®] on the list of reimbursed proprietary medicinal products in NS children with short stature (< -2 SDS)(1). The CT has recommended that Norditropin[®] treatment be initiated under following conditions:

- After resolution of feeding difficulties associated with (or not) underweight, given that these disorders are common before the age of 2. Thus, clinical data on efficacy and safety should be evaluated in paediatric patients aged at least 3 years.
- After genetic diagnosis confirmation to optimize NS management.
- At the lowest dosage of RCP (0.033 mg/kg/day). The dosage should be tailored to each patient and adjusted every six months based on clinical response (growth velocity and height) and treatment tolerance (IGF-1 monitoring).

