For incident patients, a visit schedule is provided based on the standard clinical practice for GH treatment in NS. We anticipate that each child included in this registry sees his/her enrolling physician every 6 months based on recommendations. A total of 9 visits (1 inclusion visit: D0 and 8 follow-up visits: M6, M12, M18, M24, M30, M36, M42, M48) are planned. Each visit will be allowed within one-month visit. However, no follow-up visits will be mandated by this study and the enrolling physician may not strictly comply with the schedule provided if considered as not relevant.

For prevalent patients who finished their growth upon their inclusion, all data will be collected retrospectively from medical records bi-annually from the start of Norditropin®. Visits will be referred to as V1, V2, V3... VX.

For prevalent patients who did not finish their growth upon their inclusion, data will both be collected retrospectively from medical records bi-annually from the start of Norditropin® and prospectively every 6 months following the inclusion visit.

The design of the registry is displayed in [Figure 8-1](#). This is a PASS.

Figure 8-1 Study design

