Number of modifications (change in dosage/ temporary stop)	From start of Norditropin® treatment until end of follow-up	Count of events
Reasons for treatment modifications	From start of Norditropin® treatment until end of follow-up	NA
Duration of temporary stop	From start of Norditropin® treatment until end of follow-up	Months

Title of endpoint	Time frame	Unit
Total duration of Norditropin [®] treatment	From start of Norditropin [®] treatment until end of follow-up	Years
Total cumulative dose of Norditropin [®] treatment	From start of Norditropin [®] treatment until end of follow-up	mg/kg
Other NS treatments		
Type and number of concomitant treatments	At all visits	Count of events
Type and number of concomitant treatments linked to an adverse event	At all visits	Count of events

Secondary objective-4: To describe the NS in terms of auxological characteristics, diagnosis and NS comorbidities.

The endpoints related to the secondary objective-4 are listed in [Table 6](#).

Table 6 Secondary endpoints in relation to secondary objective 4

Title of endpoint	Time frame	Unit
Auxological characteristics		
Change in weight	From start of Norditropin [®] treatment until end of follow-up	SDS
Change in body mass index (BMI)	From start of Norditropin [®] treatment until end of follow-up	Kg/m ²
Change in bone age	From start of Norditropin [®] treatment until end of follow-up	year
Change in height velocity	From start of Norditropin [®] treatment until end of follow-up	cm/year and SDS/year
Type and number of NS comorbidities	At all visits	NA

Secondary objective-5: To evaluate the evolution of Health-Related Quality of Life (HRQoL) of patients/Legally Acceptable Representative (LAR).

The endpoints related to the secondary objective-5 are listed in [Table 7](#).

Table 7 Secondary endpoint in relation to secondary objective 5

Title of endpoint	Time frame	Unit
Change in HRQoL score (PedsQL)	From start of Norditropin [®] treatment until end of follow-up	NA

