Frequency of injections per week	X	X	X	X	X	X	X	X	X
Treatment modifications (change in dosage, temporary stop)		X	X	X	X	X	X	X	X
Date of end of treatment		X							
Reasons for treatment modifications		X	X	X	X	X	X	X	X
Other GH treatments									
Previous GH treatments (type, dose at start and total duration)	X								
GH treatment following Norditropin® (type, dose and date of initiation)		X							
Other NS treatments									
Concomitant medications (with a focus on ADHD* medications including methylphenidate, cardiac medications, thyroid hormones, sex steroids comprising testosterone and oestrogens)	X	X	X	X	X	X	X	X	X
HRQoL									
PedsQL	X		X		X		X		X
Safety									
SAR, AR, SAE and AE		X	X	X	X	X	X	X	X
Pregnancy		X	X	X	X	X	X	X	X

*ADHD: Attention deficit hyperactivity disorder

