Frequency of injections per week	Categorical variable 
 • 6 days/7 • 7 days/7 • Other 	Endpoints
Type of treatment modifications	Categorical variable 
 • Increase in dosage • Decrease in dosage • Temporary stop • Permanent stop 	Endpoints
Duration of temporary stop	Continuous variable	Endpoints
Number of treatment modifications	Categorical variable 
 • From 1 to 5 	Endpoints
Reasons for treatment modifications	Categorical variable 
 • Safety (occurrence of ARs or AEs) • Growth too fast • Growth too slow • Patient's or parents/LAR choice • Other 	Endpoints
Type of previous GH treatments	Categorical variable	Endpoints
Dose of previous GH treatment at start	Continuous variable	Endpoints
Total duration of previous GH treatment	Continuous variable From start of previous GH treatment until the end of treatment	Endpoints
Type of GH treatment following Norditropin®	Categorical variable	Endpoints
Dose of GH treatment following Norditropin®	Continuous variable	Endpoints
Date of GH treatment following Norditropin®	Continuous variable	Endpoints
Concomitant medications	Categorical variable 
 • ADHD medications including methylphenidate • Cardiac medications • Thyroid hormones • Sex steroids including testosterone and oestrogen 	Endpoints

Variables	Operational Definition	Measurement
	
 Other 	
HRQoL		
PedsQL score	Categorical variable 
 From 0 to100 	Endpoints
Safety		
Incidence rate	Number of new cases per population at risk over the follow-up period (per person-time)	Endpoints
Other co-variates (controls)		
Sites 'geographic location	Categorical variable : 
 Ile-De France North-West West East South-East South-West 	Bias
Sites 'activity size s	Continuous variable Defined by the number of children treated with Norditropin® for short stature due to NS managed over a year	Bias

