8.5 Study sample size

This study will set up a registry that aims to include all eligible patients treated by Norditropin® for short stature due to Noonan syndrome.

No sample size calculation is required as this registry aims to include all patients fulfilling the sets of selection criteria defined.

According to experts' input, a maximum of 50 eligible incident patients could be included during the 24 months inclusion period. It is expected that the number of eligible patients initiating Norditropin® before 2020 would be lower since that there was no market authorisation for this indication yet and would not exceed 30 patients per year. Considering that eligible prevalent patients initiated Norditropin® from 2010, that 79% of solicited sites will be participating in the study (30 sites over 38) and that 80% of eligible patients will be included (excluding opposition, patient not regularly followed by this site), it is estimated that a maximum of 221 patients will be included in the registry.

Finally, the proportion of evaluable patients for the primary criteria (patients that have height measurements until the end of their 4 years follow-up or adult height) is planned to be 80%. Therefore, it is estimated that this study will enrol a maximum of 177 patients evaluable for the primary criteria.

The height variation (in SDS) after 4 years of treatment has been evaluated in the ANSWER® Program (observational study) at 1,14 (0,13) SDS. The change in height SDS is estimated with a 11,4% coefficient of variation (ratio of standard deviation over mean).

The following table presents the precision in primary criteria measurement (with a 2-sided 95% confidence interval (CI)) for the estimation of mean height variation in SDS considering a 20% coefficient of variation. The primary criteria will be estimated with a 2.95% precision. This high level of precision enables to perform subgroup analysis with also a satisfying precision.

Table 11 Precision of the primary criteria depending on the number of evaluable patients

Sample size	150	160	170	177	190	200
Precision for 95% CI	3.2%	3.1%	3.0%	2.95%	2.85%	2.78%

The sample size (n) is calculated based on the normal approximation using the following formula:

$$N = z_{1-\alpha/2}^2 \frac{cv^2}{\epsilon^2}$$

where:

- z is the standard normal distribution's quantile (for $\alpha=5\%$),
- CV is the coefficient of variation (20%),

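### Table 10 restricts the number of treatment modifications to 1 to 5, which contradicts the open event count in Table 5, and its reason list has no code for IGF-1 or end of growth (minor)

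*Protocol*

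**What the plan says.** Describing GH treatment patterns is part of a secondary objective (Protocol section 7.2). Four places bear on how modifications are recorded.

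- **Table 5 (section 8.1.1.2)** lists "Number of modifications (change in dosage/ temporary stop" as an endpoint. Its unit is an event count and its time frame runs from treatment start to end of follow-up. No upper limit is given.
- **Table 10 (section 8.3)** makes the number of treatment modifications a categorical variable with values 1 to 5. The modification types are dose increase, dose decrease, temporary stop and "Permanent stop". The reasons are "Safety (occurrence of ARs or AEs) • Growth too fast • Growth too slow", then patient or parent/LAR choice, then a residual class.
- **Table 9 (section 8.2.8.1, flow chart)** schedules "Treatment modifications (change in dosage, temporary stop" at every follow-up visit from M6 to M48, together with the reasons. A permanent stop is not named in that row; the date of end of treatment has its own row.
- **Section 6.1** reports the Transparency Committee's recommendation that dosage be "adjusted every six months based on clinical response (growth velocity and height) and treatment tolerance (IGF-1 monitoring".

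Section 8.1 plans "8 follow-up visits: M6, M12, M18, M24, M30, M36, M42, M48" for incident children. For prevalent children who have finished growing, "data will be collected retrospectively from medical records bi-annually from the start of" treatment. Those still growing have the same retrospective collection plus six-monthly prospective visits.

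**The concern.** One endpoint has two definitions that cannot both be programmed. Under Table 5 a child never adjusted scores 0 and a child adjusted at every visit scores 8. Under Table 10 neither has a value. The share of children never adjusted is a basic result for treatment patterns, and it is the one the category leaves out at the lower end.

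Whether a permanent stop adds one to the count is also unsettled, because Table 10 includes it as a type while Table 5 and the flow chart do not name it. If it counts, each child whose treatment ends contributes one more event.

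The reason list covers growth, which section 6.1 names as one basis for adjustment, but not IGF-1, which it names as the other. Sites would have to choose between the safety class and the residual class, and may choose differently. End of growth, a foreseeable reason for stopping in a registry that follows children towards adult height, can only go to the residual class. What is at stake is how well one descriptive secondary objective can be reported.

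**Working it through.** **Inputs from the protocol.** Follow-up of 48 months with visits every 6 months (section 8.1); permitted values 1 to 5 (Table 10); event count (Table 5); for prevalent children, "Considering that eligible prevalent patients initiated Norditropin® from 2010" (section 8.5) with six-monthly data from treatment start (section 8.1); inclusion from March 2022 to March 2024 and last visit in March 2028 (Table 1).

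**Assumption, not in the protocol.** At most one modification per visit, with constant probability p, independent between visits. The protocol gives no rate, so p is varied.

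**1. Visits.** 48 / 6 = 8, which reproduces the stated number.

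**2. Where the range runs out.** A child changed at each visit reaches 5 at 5 × 6 = M30. The sixth, seventh and eighth changes, at M36, M42 and M48, have no value. For incident children the values left out are therefore 0, 6, 7 and 8.

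**3. Prevalent children, ceiling only.** For a start in 2010, the half-years available are (2022 − 2010) × 2 = 24, (2024 − 2010) × 2 = 28 and (2028 − 2010) × 2 = 36. These count occasions under uninterrupted treatment. They are not expected numbers of changes.

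**4. Share outside 1 to 5.** With V visits and X ~ Binomial(V, p), the share is P(X = 0) + P(X ≥ 6), where P(X = 0) = (1 − p)^V. For V = 8 and p = 0.25: 0.75^8 = 0.1001 and P(X ≥ 6) = 0.0042, together 0.1043.

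| p (assumed) | V = 8: zero | V = 8: six or more | V = 8: outside 1–5 | V = 16: outside | V = 24: outside |
|---|---|---|---|---|---|
| 0.10 | 43% | 0.0% | 43% | 18.9% | 10.7% |
| 0.25 | 10.0% | 0.4% | 10.4% | 20.0% | 57.9% |
| 0.50 | 0.4% | 14.5% | 14.8% | 89.5% | 99.7% |
| 0.75 | 0.0% | 67.9% | 67.9% | >99.9% | 100% |

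For V = 8 the smallest share is about 5.7%, near p = 0.35 (0.65^8 = 0.032 plus P(X ≥ 6) = 0.025). Under this model some children with eight visits lack a valid code whatever the rate.

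**5. Event types and reasons, side by side.** Dose change and temporary stop appear in Tables 5, 9 and 10; permanent stop as a modification appears only in Table 10. Of the bases for adjustment in section 6.1, growth velocity and height have a matching reason code and IGF-1 has none. Appendix A includes an abnormal laboratory finding in its definition of an adverse event, so a change prompted by an abnormal IGF-1 can be filed under safety. A change prompted by an IGF-1 value that is not abnormal has no clear place.

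**The case against.** The strongest reply is that this is a labelling slip with little loss of data. Dose is recorded at each visit, and titration, modifications and reasons are scheduled from M6 to M48, so the count, zeros included, could be rebuilt. Table 10 is loose elsewhere too: it calls the 0-to-100 PedsQL score categorical. It does not say whether 1 to 5 applies per visit or per child. The pick-lists sit in the CRF, a stand-alone document that is not shown and may have a free-text field. Much of this stands and is why the point is minor. It does not remove the contradiction: Table 5 runs over the whole treatment period, and on either reading 0 is missing.

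A reader might infer more than the documents support:

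- *That the treatment-pattern endpoints in general are truncated.* They are not. Dose, cumulative dose, treatment duration and duration of temporary stop are continuous and uncapped.
- *That coding an IGF-1-driven change as safety is an error that inflates safety modifications.* Appendix A permits it for an abnormal value, and section 6.1 treats IGF-1 as a tolerance measure. The defect is ambiguity.
- *That the registry can say nothing about IGF-1 and dosing.* IGF-1 is scheduled at every visit alongside dose, so the two can be tabulated together. Only the physician's stated reason is missing.
- *That all end-of-growth stops are lost, or that end of growth is the commonest reason for stopping.* The protocol says neither. Date of end of treatment and adult height are collected separately, so most such stops should be identifiable.
- *That 24 or 36 modifications are to be expected.* These are ceilings. They also carry an October 2020 recommendation back to 2010.

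**Conclusion.** The point holds as a minor inconsistency in one descriptive secondary variable. Table 10 and Table 5 define the number of modifications incompatibly, and the Table 10 range has no value for children with 0 or more than 5. Whether a permanent stop counts is undefined. The reason list lacks IGF-1 and end of growth, which invites inconsistent coding but does not by itself make any code wrong.

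The contradiction and the omitted values follow from the text alone. Their size does not: the range of about 6% to 68% for eight visits rests on assumed rates up to 0.75 per visit, independence, and at most one change per visit. In incident children the upper limit bites only if changes are frequent (0.4% exceed five at p = 0.25, 14.5% at p = 0.50); when changes are rare the missing zero is the problem. The primary endpoint and the adverse-event incidence analyses are not touched.

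**What to change.** 1. In Table 10, define the number of modifications as an uncapped count including 0, derived from the visit records, in line with Table 5.
2. Use one list of event types in Tables 5, 9 and 10, and state whether a permanent stop counts as a modification.
3. Add two reason codes, one for IGF-1 level and one for end of growth or adult height reached. Add a completion note on when an IGF-1-driven change is coded as safety, consistent with the adverse-event definition in Appendix A.

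The cost is a few eCRF pick-list entries and matching edits to three tables, with no extra visits or tests. It is best done before data entry begins: the count could be rebuilt later, but reasons filed inconsistently would probably need a return to the medical records.

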8.4 Data sources

The data required to address the registry objectives come from the medical records, prescription records, laboratory and questionnaires administered to patients (patient reported outcomes-PROs). Study investigators (or clinical research associates (CRAs)) will capture data through an e-CRF.

HRQoL will be collected directly from incident patients and their parents by using a self-administered validated quality of life questionnaires (PedsQL). They will complete the questionnaires independently from physicians.

Data will be collected as per routine practice. If the data is not available, it will not be required and collected.

8.5 Study sample size

This study will set up a registry that aims to include all eligible patients treated by Norditropin® for short stature due to Noonan syndrome.

No sample size calculation is required as this registry aims to include all patients fulfilling the sets of selection criteria defined.

According to experts' input, a maximum of 50 eligible incident patients could be included during the 24 months inclusion period. It is expected that the number of eligible patients initiating Norditropin® before 2020 would be lower since that there was no market authorisation for this indication yet and would not exceed 30 patients per year. Considering that eligible prevalent patients initiated Norditropin® from 2010, that 79% of solicited sites will be participating in the study (30 sites over 38) and that 80% of eligible patients will be included (excluding opposition, patient not regularly followed by this site), it is estimated that a maximum of 221 patients will be included in the registry.

Finally, the proportion of evaluable patients for the primary criteria (patients that have height measurements until the end of their 4 years follow-up or adult height) is planned to be 80%. Therefore, it is estimated that this study will enrol a maximum of 177 patients evaluable for the primary criteria.

The height variation (in SDS) after 4 years of treatment has been evaluated in the ANSWER® Program (observational study) at 1,14 (0,13) SDS. The change in height SDS is estimated with a 11,4% coefficient of variation (ratio of standard deviation over mean).

The following table presents the precision in primary criteria measurement (with a 2-sided 95% confidence interval (CI)) for the estimation of mean height variation in SDS considering a 20% coefficient of variation. The primary criteria will be estimated with a 2.95% precision. This high level of precision enables to perform subgroup analysis with also a satisfying precision.

Table 11 Precision of the primary criteria depending on the number of evaluable patients

Sample size	150	160	170	177	190	200
Precision for 95% CI	3.2%	3.1%	3.0%	2.95%	2.85%	2.78%

The sample size (n) is calculated based on the normal approximation using the following formula:

$$N = z_{1-\alpha/2}^2 \frac{cv^2}{\epsilon^2}$$

where:

- z is the standard normal distribution's quantile (for $\alpha=5\%$),
- CV is the coefficient of variation (20%),
- ϵ is the precision (i.e., ratio of the mean estimation that determines half width of the 95% CI).

8.6 Data management

██████ on behalf of Novo Nordisk will be responsible for the management of data collected in this study.

Novo Nordisk will provide electronic Case Report Forms (eCRFs) for capture of study specific patient data. Instructions for completion and correction of eCRF will be provided in the eCRF completion guidelines.

The physician must ensure that study specific patient data is entered in the eCRF according to the visits schedule (see [Table 9](#)), as much as possible. When data is entered it will be available to Novo Nordisk for data verification activities. Appropriate measures such as encryption or deletion must be enforced to protect the identity of patients when transmitting data, in all presentations and publications as required by local/regional/national requirements.

For eCRFs: The system for Electronic Data Capture (EDC) and support services for the system will be supplied by [REDACTED]. The activities of [REDACTED] will be under the direction and supervision of Novo Nordisk.

An audit trail will be maintained in the EDC application containing as a minimum: identification of the person entering the data, date and time of the entry and reason for the correction, the original entry and the corrected entry.

By signing the affirmation statement/casebook the physician confirms that the information in the eCRF is complete and correct. The physician has the responsibility to maintain adequate and accurate information entered in the eCRF.

If corrections are made by the physician's authorised staff after the date of the physician's signature on the affirmation statement/casebook, this must be signed again by the physician.

8.7 Data analysis

8.7.1 Definition of analysis sets

The site populations will be defined as follows:

- Contacted sites: all reference and competence centres in France will be solicited to participate in this study
- Participating sites: all sites that agreed to participate in the study
- Active sites: all sites that included at least one eligible patient

The sites main characteristics (localisation, size) will be compared to ensure that the active sites are representative at the national level.

There are 3 patients population considered in this study:

- Overall population: all patients included in the eCRF,
- Full Analysis Set (FAS): all patients included in the eCRF and meeting all selection criteria. All secondary analyses will be performed on FAS.

- Growth Analysis Set (GAS): all patients from the FAS for which the primary criteria can be evaluated, i.e. height measurements available until the end of the 5-year follow-up or until NAH is reached, whatever occurs first.

The subgroups of interest for analyses are defined as follows:

- Norditropin[®] treatment duration: depending on age of onset and age at puberty onset, the patients may have shorter or longer time under GH treatment, which may highly influence auxological outcomes
- Mutated gene: PTPN11, SOC2, other

